5.1.3 Cisplatin

The cytotoxicity of cisplatin might be due to its ability to crosslink different DNA stands. Thus DNA replication is inhibited. Nevertheless, the mechanism of how platinum-caused DNA defects can lead to cell death is not yet known in detail.

Cisplatin is one of the most effective and most frequently applied substances in the treatment of metastasized and advanced gastric cancers. It is the basis of different combination regimes like ECF (epirubicin, cisplatin, 5-FU), FUP (5-FU, cisplatin), MCF (mitomycin, cisplatin, 5-FU), EAP (Etoposid, Doxorubicin, Cisplatin) FLEP (5-FU, folinic acid, etoposid, cisplatin) or FLP (5-FU, folinic acid, cisplatin).

In this trial commercially available cisplatin will be used. Investigators should refer to the respective Summary of Product Characteristics (SmPC) for complete prescription information such as dosage and administration, safety issues (warning, precautions), adverse reactions, dose modifications and omissions and storage information. Investigators should also follow institutional procedures for the administration of cisplatin.

Cisplatin will be administered after saline hydration as intravenous bolus infusion on days 1-4 at the beginning of each course. The saline hyperhydration will be given according to the investigational centre's routine.

All subjects must receive adequate anti-emetic therapy prior to the administration of cisplatin. It is recommended that a 5HT3 antagonist (e.g. Granisetron) and dexamethasone 8mg i.v. are administered prior to each cycle of treatment.

5.2.2 Blinding

Not applicable

5.2.3 Procedure for emergency code-breaks

Not applicable

5.3 Special precautions

5.3.1 Cetuximab administration

Allergic/Hypersensitivity reactions

Allergic/Hypersensitivity reactions may occur during or following the administration of cetuximab. Subjects must therefore be pretreated with an appropriate antihistamine and a glucocorticoid before the first infusion. Pretreatment with an antihistamine and a glucocorticoid is recommended before subsequent infusions. As a routine precaution, subjects enrolled into this study should be observed closely for any potential AEs and a physician able to give emergency medical treatment must be present from the start of cetuximab infusion until at least 1 hour after the end of the infusion. The subject should be observed in an area with resuscitation equipment and other agents available (epinephrine, prednisolone equivalents etc). Should an allergic/hypersensitivity or infusion reaction to cetuximab occur, then the subject must be treated according to the best available medical practices. For adjustment of cetuximab treatment, see section 5.4.1. Grade 3 or 4 allergic/hypersensitivity reactions require immediate interruption of the cetuximab infusion, appropriate medical measures and permanent discontinuation of treatment. Subjects should be carefully monitored until the complete resolution of all signs and symptoms.

Skin reactions

The most common AE associated with cetuximab administration are skin reactions, particularly acne-like rash. If a subject experiences a grade 3 skin reaction, cetuximab therapy must be interrupted for up to 2 consecutive weeks. Treatment may only be resumed, if the reaction has resolved to grade 2. For recommended adjustments in dose regimen, see section 5.4.1. If grade 3 skin reactions occur a fourth time or do not resolve to grade ≤ 2 during treatment interruption, permanent discontinuation of cetuximab treatment is required.

Interstitial pneumonitis

Severe interstitial pneumonitis has been described in subjects treated with the EGFR-pathway targeting therapy gefitinib. To date, no increased risk of interstitial pneumonitis has been identified with cetuximab. Nevertheless, all subjects must have adequate chest imaging prior to commencing cetuximab therapy in the study, as a safety precaution in order to document the baseline pulmonary condition. If there are respiratory symptoms at study entry, lung function tests and further diagnostic procedures must also be undertaken in order to diagnose pre-existing pulmonary fibrosis or interstitial pneumonitis. Furthermore, subjects will be regularly questioned about pulmonary symptoms during the study. Should pulmonary symptoms appear or worsen during or after cetuximab treatment, a detailed description is required and investigators should use their discretion in ordering such diagnostic procedures as are necessary to elicit an accurate diagnosis.

Electrolyte disturbances

Progressively decreasing serum magnesium levels occur frequently and may lead to severe hypomagnesaemia. Hypomagnesaemia is reversible following discontinuation of cetuximab. In addition, hypokalaemia may develop as a consequence of diarrhoea. Hypocalcaemia may also occur; in particular in combination with platinum-based chemotherapy the frequency of severe hypocalcaemia may be increased. Determination of serum electrolyte levels is recommended prior to and periodically during cetuximab treatment. Electrolyte repletion is recommended, as appropriate.

Neutropenia and related infectious complications

Patients who receive cetuximab in combination with platinum-based chemotherapy are at an increased risk for the occurrence of severe neutropenia, which may lead to subsequent infectious complications such as febrile neutropenia, pneumonia or sepsis. Careful monitoring is recommended in such patients, in particular in those who experience skin lesions, mucositis or diarrhoea that may facilitate the occurrence of infections.

Cardiovascular disorders

An increased frequency of severe and sometimes fatal cardiovascular events and treatment emergent deaths has been observed in the treatment of non-small cell lung cancer, squamous cell carcinoma of the head and neck and colorectal carcinoma. In some studies (non-small cell lung cancer) association with age ≥ 65 years has been observed. When prescribing cetuximab, the cardiovascular status of the patients and concomitant administration of cardiotoxic compounds such as fluoropyrimidines should be taken into account.

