4.2.4 Removal of patients from the study or study treatment

Patients are free to discontinue the study at any time without giving their reason(s).

The patient must be withdrawn from study treatment in the event of any of the following:

- Withdrawal of the patient's consent
- Occurrence of an exclusion criterion which is clinically relevant and affects the patient's safety
- Occurrence of AEs, if discontinuation is desired or considered necessary by the patient and/or investigator
- Occurrence of pregnancy during treatment
- Lack of subject compliance
- A delay of treatment with cetuximab for more than 2 consecutive weeks
- Occurrence of any grade 4 toxicities related to cetuximab
- Occurrence of \geq grade 3 allergic/hypersensitivity reaction related to cetuximab
- Occurrence of disease progression

If there is a medical reason for withdrawal, the patient will remain under the supervision of the investigator until the AEs have been resolved or declined to baseline values.

If a patient has failed to attend scheduled assessments in the study, the investigator must determine the reasons and circumstances as completely and accurately as possible.

In case of premature discontinuation of the study treatment by a patient, the investigations scheduled for the last visit should be performed, if possible. In any case, the CRF section entitled "End of Treatment" must be completed.

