5.4.1.1 Skin toxicities

If a subject experiences a grade 3 skin toxicity (as defined in the US National Cancer Institute's - Common Toxicity Criteria [NCI-CTC], Version 4.0), cetuximab therapy may be delayed for up to two consecutive infusions without changing the dose level. For grade 1 or 2 acne-like rash treatment with topical antibiotics (e.g. benzoylperoxide, erythromycin) or systemic antibiotics (e.g. oral tetracyclines such as doxycycline 100 mg od) should be considered. Patients with grade ≥ 3 reactions should be referred to the dermatologist for advice and management. If pruritus occurs an oral antihistamine is advised. In case of dry skin the use of emollient creams is beneficial. Fissures may occur in dry skin and topical dressings are helpful. If the toxicity resolves to grade 2 or less by the following treatment period, treatment may resume. With the second and third occurrences of grade 3 skin toxicity, cetuximab therapy may again be delayed for up to two consecutive weeks with concomitant dose reductions to 200 mg/m² and 150 mg/m², respectively. Cetuximab dose reductions are permanent. Subjects should discontinue cetuximab if more than two consecutive infusions are withheld or a fourth occurrence of a grade 3 skin toxicity occurs despite appropriate dose reduction (see figure 1).

However, if in the opinion of the investigator the discontinuation of cetuximab is considered necessary, the subject should be withdrawn immediately.

The dose of cetuximab will be adjusted for cetuximab-related grade 3 skin toxicities only. Cetuximab therapy will not be withheld for chemotherapy related toxicities. Therefore, in the event that the next infusion of chemotherapy is delayed, the subject will receive cetuximab as previously planned.

Figure 1: Treatment adjustment in the event of grade 3 skin toxicity considered to be related to cetuximab.

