Grade-specific management approaches	
 Weekly follow-up is adequate, unless rapid progression is noted 	
 Consider twice-weekly assessments to monitor for rapid change A. Dry desquamation without crusts: 
 Consider glucocorticosteroid cream or ointment for a limited period (1–2 weeks) Topical antiseptics and antibiotics at any sign of superinfection Consider the use of topical antiseptics and antibiotics for the prevention of more severe reactions B. Moist desquamation in skin folds: 
 Topical antiseptic Consider adding daily topical glucocorticosteroid lotion to reduce inflammation for a limited period (1–2 weeks) Topical antibiotics 	
 Evaluate the need for daily assessment Closely monitor for signs of local or systemic infection For grade 3 reactions occurring at <50 Gy, consider brief interruption in treatment A. Confluent moist desquamation without crusts: 
 Topical antiseptic Consider adding daily topical glucocorticosteroid lotion to reduce inflammation for a limited period (1–2 weeks) Topical antibiotics active against S. aureus at any sign of superinfection If superinfection becomes more severe, consider the use of i.v. antibiotics if unresponsive to oral antibiotics 	
 Consider interrupting treatment with both radiotherapy and cetuximab. Cetuximab should be interrupted until the skin reaction has resolved to at least grade 2 In the case of severe superinfection, consider the use of i.v. antibiotics if unresponsive to oral antibiotics Hospitalize the patient

Grade of dermatitis associated with radiation-based therapy

Grade 1	Grade 2 ^a	Grade 3 ^a	Grade 4 ^a

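### Grade 3 skin reactions: holding cetuximab is mandatory in 5.3.1 but permissive in 5.4.1.1; at grade 4, section 4.2.4 and the Appendix 5 table collide only for events judged cetuximab-related

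*Combined protocol and SAP*

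**What the plan says.** **Grade 3.** Section 5.3.1, under skin reactions, states that "cetuximab therapy must be interrupted for up to 2 consecutive weeks" and that "Treatment may only be resumed, if the reaction has resolved to grade 2". It sends the reader to 5.4.1 for dose adjustment. Section 5.4.1.1 covers the same event. At the first occurrence, "cetuximab therapy may be delayed for up to two consecutive infusions without changing the dose level", and "If the toxicity resolves to grade 2 or less by the following treatment period, treatment may resume". Later: "With the second and third occurrences of grade 3 skin toxicity, cetuximab therapy may again be delayed for up to two consecutive weeks", with permanent dose reductions attached. Both sections end cetuximab at a fourth occurrence. Section 5.4.1.1 also points to a Figure 1 on grade 3 skin toxicity related to cetuximab; its content is not reproduced in the text available for this review.

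**Grade 4.** Section 4.2.4 opens its list with "The patient must be withdrawn from study treatment in the event of any of the following". One item is "Occurrence of any grade 4 toxicities related to cetuximab". Section 5.4.1.1 limits cetuximab dose adjustment to grade 3, so it does not address grade 4. The grade 4 column of the table under the Appendix 5 heading advises considering an interruption of both radiotherapy and cetuximab, and adds: "Cetuximab should be interrupted until the skin reaction has resolved to at least grade 2". The table's own title limits it to radiation dermatitis in patients treated with cetuximab and radiotherapy together.

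**The concern.** Skin reactions are described in the protocol as the most common adverse events of cetuximab, so the rule for holding the drug will be consulted in practice. If one section commands a hold and another only allows it, an investigator who infuses without a hold can cite 5.4.1.1 while departing from 5.3.1. A monitor could then either record a deviation or not, depending on which section is open. With approximately 15 centres planned, handling could differ between sites. What is at stake is the safety rule itself and uniform cetuximab exposure within Arm A. At grade 4 the worry is similar: one text ends study treatment and another leaves room to restart cetuximab.

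**Working it through.** No sample size, power or event count enters this point, so there is no figure to reproduce. The check sets the texts side by side.

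**Grade 3**

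| Element | 5.3.1 | 5.4.1.1 | Same? |
|---|---|---|---|
| Is a hold required? | *must* | *may*; *may again* at occurrences 2 and 3 | No |
| Longest hold | 2 consecutive weeks | 2 consecutive infusions (occurrence 1); 2 consecutive weeks (occurrences 2 and 3) | Yes, as infusions are weekly |
| Recovery before resuming | grade 2 (its next lines use grade 2 or lower) | grade 2 or lower | Yes |
| Permanent stop | fourth occurrence, or no recovery during the interruption | fourth occurrence, or more than two consecutive infusions withheld | Fourth-occurrence stop agrees |

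Only the first row differs. Because 5.3.1 refers onward to 5.4.1, both sections govern the same event, and no sentence ranks one above the other.

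**Grade 4**

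1. Section 4.2.4 is triggered by a grade 4 toxicity related to cetuximab. Its consequence is mandatory withdrawal from study treatment.
2. The Appendix 5 table is triggered by grade 4 dermatitis under radiotherapy combined with cetuximab. Its consequence is a hold until recovery to at least grade 2, which only makes sense if resumption is possible.
3. If the dermatitis is attributed to radiotherapy alone, the 4.2.4 item is not triggered and there is no conflict.
4. If it is judged related to cetuximab, both triggers are met and the consequences differ.
5. Arm A gives the two treatments concurrently, so case 4 can arise.

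Two features of the table add to the need to state its scope. Its grade 3 column has another formulation, a suggestion to consider a short interruption for reactions below 50 Gy. It also prints a proposed modification of the CTCAE v4.03 grading, while 5.4.1.1 grades by NCI-CTC version 4.0, so one reaction might be graded differently under the two.

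**The case against.** The strongest reply is that these are differences in strictness rather than incompatible orders. A reader might infer that a site cannot comply with every section at once. The documents do not support that: a hold satisfies both grade 3 texts, since what one requires the other permits, and withdrawal at grade 4 is not forbidden by a table that speaks of considering interruption. This part stands, as a remark on logical compatibility and not as a view on which rule is right.

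A reader might also infer that 5.4.1.1 lets a patient continue at full dose through a grade 3 reaction. Its surrounding text weighs against that. The resumption sentence presupposes a hold, dose reductions attach to the second and third occurrences, and reactions of grade 3 or above go to a dermatologist. The permissive verb may have been meant to cap the length of the hold. That is a plausible reading, but 5.4.1.1 does not say so. Figure 1 may state the hold plainly; it could not remove the difference between the two sections' prose, but it must be part of any reconciliation.

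For grade 4, the reply is that the texts describe different events. The protocol does separate causes: Table 3 lists the irradiated region and cetuximab-related skin toxicity separately, and section 6.1.2 requires a causality judgement for each event. The table may also be misplaced. It is marked as an English version for registry presentation, and Appendix 6, whose title names radiation dermatitis, is printed without content. So the Appendix 5 heading should carry little weight, and a general conflict at grade 4 is not shown. What remains is the overlap for events judged related to cetuximab, which does not depend on the heading.

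**Conclusion.** The point holds as an internal inconsistency in an operative safety rule, minor in extent and curable by wording. At grade 3 the sections disagree on one thing only, whether the hold is obligatory. At grade 4 the disagreement is conditional on attribution to cetuximab.

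No patient count can be attached. A reader might multiply the figures in section 2.3.2.3 (skin reactions in more than 80% of patients, about 15% of the reactions severe) to get an expected number in Arm A. That section itself warns that rates from such different trials cannot validly be pooled, and the 15% is a share of reactions, not of patients.

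Different handling between sites is an inference from the wording and the number of centres; nothing in the documents shows that it occurred. The effect on the primary estimate should be limited, because the per-protocol set in section 8.1 keeps patients who stop early for toxicity. The conclusion assumes that Figure 1 does not establish an order of precedence.

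**What to change.** Reconcile sections 4.2.4, 5.3.1 and 5.4.1.1 (with Figure 1) and the Appendix 5 table so that each grade of skin reaction has one rule. State whether the table applies to radiation dermatitis only, which grading system triggers each rule, how a grade 4 skin event related to cetuximab within the irradiated area is to be classified, and which text prevails if any difference remains. The sponsor decides the clinical content; none is proposed here.

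The cost is protocol wording, documented in writing as section 12.5 requires for formal clarifications as well as changes. Sample size and analysis are untouched. As an inexpensive check, the CRF already records the action taken on cetuximab for each adverse event (section 6.1.2), so a listing of Arm A grade 3 and 4 skin events by centre would show whether handling in fact differed.

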5.3.2 Chemotherapy administration

5-Fluorouracil and cisplatin are commercially available antineoplastic agents. Investigators should use the approved package inserts of these drugs for complete prescribing information, including any special precautions.

5.4 Selection, timing and modification of dose for each patient

5.4.1 Cetuximab

Patients will receive 14 weekly infusions with cetuximab. If a patient has to receive 5-FU and cisplatin at the same day, they should be administered after a 1-hour observation period post cetuximab infusion.

For all patients, the dosage and administration procedure for cetuximab is as follows:

Initial dose:

The total **initial dose** (first infusion) is **400 mg/m² (80 mL/m² ready-to-use solution)** and is administered over a period of 120 minutes (maximum infusion rate of 10 mg/min, corresponding to 2 mL/min ready-to-use solution). Patients must be pre-treated with an antihistamine as well as a glucocorticoid. Observe the patient during infusion and for one hour afterwards. Check the vital signs pre-, mid-, post- and one hour post-infusion. Use a sterile 0.9% NaCl solution to flush the line at the end of infusion.

Further infusions:

[figure not shown]
The **weekly dose** (all further infusions) is **250 mg/m² (= 50 mL/m² ready-to-use solution)** and is administered over a period of 60 minutes (maximum infusion rate of 10 mg/min, corresponding to 2 mL/min ready-to-use solution). It is recommended that the patient is pre-treated with an antihistamine as well as a glucocorticoid prior to each infusion. Observe the patient during infusion and for one hour afterwards. Check the vital signs pre-, mid-, post- and one hour post-infusion. Use a sterile 0.9% NaCl solution to flush the line at the end of infusion.

5.4.1.1 Skin toxicities

If a subject experiences a grade 3 skin toxicity (as defined in the US National Cancer Institute's - Common Toxicity Criteria [NCI-CTC], Version 4.0), cetuximab therapy may be delayed for up to two consecutive infusions without changing the dose level. For grade 1 or 2 acne-like rash treatment with topical antibiotics (e.g. benzoylperoxide, erythromycin) or systemic antibiotics (e.g. oral tetracyclines such as doxycycline 100 mg od) should be considered. Patients with grade ≥ 3 reactions should be referred to the dermatologist for advice and management. If pruritus occurs an oral antihistamine is advised. In case of dry skin the use of emollient creams is beneficial. Fissures may occur in dry skin and topical dressings are helpful. If the toxicity resolves to grade 2 or less by the following treatment period, treatment may resume. With the second and third occurrences of grade 3 skin toxicity, cetuximab therapy may again be delayed for up to two consecutive weeks with concomitant dose reductions to 200 mg/m² and 150 mg/m², respectively. Cetuximab dose reductions are permanent. Subjects should discontinue cetuximab if more than two consecutive infusions are withheld or a fourth occurrence of a grade 3 skin toxicity occurs despite appropriate dose reduction (see figure 1).

However, if in the opinion of the investigator the discontinuation of cetuximab is considered necessary, the subject should be withdrawn immediately.

The dose of cetuximab will be adjusted for cetuximab-related grade 3 skin toxicities only. Cetuximab therapy will not be withheld for chemotherapy related toxicities. Therefore, in the event that the next infusion of chemotherapy is delayed, the subject will receive cetuximab as previously planned.

Figure 1: Treatment adjustment in the event of grade 3 skin toxicity considered to be related to cetuximab.

5.4.1.2 Allergic/hypersensitivity reactions

In each case of allergic/hypersensitivity reaction, the investigator should implement treatment measures according to the best available medical practice. Based on previous experience with cetuximab allergic/hypersensitivity reactions, the treatment guidelines as described in Table 2 may be applicable.

Table 2 Treatment adjustment in the event of cetuximab caused allergic / hypersensitivity reaction.

CTC Grade Allergic/ Hypersensitivity Reaction	Treatment
Grade 1	Decrease the cetuximab infusion rate by 50% and monitor closely for any worsening. The total infusion time for cetuximab should not exceed 4 hours.
Grade 2	Stop cetuximab infusion. Administer bronchodilators, oxygen, etc. as medically indicated. Resume infusion at 50% of previous rate once allergic/hypersensitivity reaction has resolved or decreased to Grade 1 in severity, and monitor closely for any worsening
Grade 3 or Grade 4	Stop the cetuximab infusion immediately and disconnect infusion tubing from the subject. Administer epinephrine, broncho- dilators, antihistamines, glucocorticoids, intravenous fluids, vasopressor agents, oxygen, etc., as medically indicated. Subjects must be withdrawn immediately from the

	treatment and must not receive any further cetuximab treatment.
--	--

Re-treatment following allergic/hypersensitivity reactions:

Once a cetuximab infusion rate has been decreased due to an allergic/hypersensitivity reaction, it will remain decreased for all subsequent infusions. If the subject has a second allergic/hypersensitivity reaction with the slower infusion rate, the infusion should be stopped and the subject should be removed from the study. If a subject experiences a Grade 3 or 4-allergic/hypersensitivity reactions at any time, cetuximab should be discontinued.

